7.2 Handling of Missing and Incomplete Data

Missing clinical outcome data can occur for multiple reasons, including missed subject visits and scales or measures with missing item scores. Missing and incomplete data will be identified through a review of tables and listings for this study. Missing and incomplete data will be identified for investigation, and possible resolution, by Data Management prior to the study database lock.

Missing or invalid safety events and assessments will not be imputed or replaced. Missing measurements in HHD individual muscle group test will be imputed as 0 if the reason for missing is due to weakness. When the measurement for one side is missing, the measurement from the other side will be used to impute the missing value. Details of missing observation handling in HHD are provided in Appendix 10.3. Other efficacy endpoints will not be imputed.

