8.8 Efficacy Analyses

For each efficacy endpoint, summary statistics will be reported at each visit for the observed measures and their respective changes from baseline.

The efficacy endpoints measured over time will be analyzed using GEE using the Full Analysis Set. Changes from baseline will be the dependent variable, and baseline, visit will be the independent variables in the model. All efficacy endpoints were assessed at Baseline, Week 12, Week 24, Week 36, and Week 48.

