10.1.2 Short Form – 36 Item (SF-36)

The SF 36 will be completed by subjects at each visit beginning with the Baseline Visit to assess physical and mental health based on 8 scaled scores that are the weighted sums of the questions in their section: vitality, physical functioning, bodily pain, general health perceptions, physical role functioning, emotional role functioning, social role functioning, and mental health. Each scale is directly transformed into a 0 to 100 scale on the assumption that each question carries equal weight. Lower scores indicate more diminished health-related quality of life.

The scale and component scores will be calculated according to the standard scoring algorithm published along with the SF-36 (Ware et.al. 1995 and Ware et.al. 2007). The z

scores of domain scales will be aggregated to generate the component scores PCS and MCS using weights derived from the U.S. general population. The component scores will be scaled to have a mean of 50 and standard deviation of 10 using a linear transformation. The component scores will not be calculated unless all relevant domain scale scores are available. Details of the scoring algorithm can be found in Appendix [10.4](#).

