10.4 SF-36 v2® Scoring Algorithm

Prior to any summary scores being calculated, ten items in the questionnaire will be re-coded according to the developer's instructions as follows:

	Response Choices	Pre-coded Item Value		Final Item Value
Item 1	Excellent	1		5.0
	Very Good	2		4.4
	Good	3		3.4
	Fair	4		2.0
	Poor	5		1.0
Item 6	Not At All	1		5
	Slightly	2		4
	Moderately	3		3
	Quite A Bit	4		2
	Extremely	5		1
Item 7	None	1		6.0
	Very Mild	2		5.4
	Mild	3		4.2
	Moderate	4		3.1
	Severe	5		2.2
Item 8	If both item 7 and item 8 are answered	Item 8 pre-coded value	Item 7 pre-coded value	
	Not At All	1	1	6
	Not At All	1	2 through 6	5
	A Little Bit	2	2 through 6	4
	Moderately	3	2 through 6	3
	Quite A Bit	4	2 through 6	2
	Extremely	5	2 through 6	1

	Response Choices	Pre-coded Item Value	Final Item Value
Item 8	If Item 7 is not answered		
	Not At All	1	6.0
	A Little Bit	2	4.75
	Moderately	3	3.5
	Quite A Bit	4	2.25
	Extremely	5	1.0
Item 9a, 9d, 9e and 9h	All Of The Time	1	6
	Most Of The Time	2	5
	A Good Bit Of The Time	3	4
	Some Of The Time	4	3
	A Little Of The Time	5	2
	None Of The Time	6	1
Item 11b and 11d	Definitely True	1	5
	Mostly True	2	4
	Don't Know	3	3
	Mostly False	4	2
	Definitely False	5	1

Upon appropriate re-coding of individual items, the raw scale score will be calculated as the average score over non-missing items in that scale and scaled between 0 and 100, with higher score representing better health status. The raw scale score will not be calculated unless $\geq 50\%$ of relevant questions are answered in a scale domain.

The raw scale scores will be computed by taking the sum of the items for that particular scale. Each raw scale score will then be transformed to a 0 to 100 scale using the following formula:

$$\text{Transformed Scale} = \frac{[\text{Actual raw score} - \text{Lowest possible raw score}]}{\text{Possible raw score range}} \times 100$$

This information is summarized in the following table.

Formulae for Scoring and Transforming Scales			
Scale	Sum Final Item Values	Lowest And Highest Possible Raw Scores	Possible Raw Score Range
Physical Functioning (PF)	$3a + 3b + 3c + 3d + 3e + 3f + 3g + 3h + 3I + 3j$	10, 30	20
Role-Physical (RP)	$4a + 4b + 4c + 4d$	4, 8	4
Bodily Pain (BP)	$7 + 8$	2, 12	10
General Health (GH)	$1 + 11a + 11b + 11c + 11d$	5, 25	20
Vitality (VT)	$9a + 9e + 9g + 9i$	4, 24	20
Social Functioning (SF)	$6 + 10$	2, 10	8
Role-Emotional (RE)	$5a + 5b + 5c$	3, 6	3
Mental Health (MH)	$9b + 9c + 9d + 9f + 9h$	5, 30	25

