A norm-based z score for each scale will then be computed using the U.S. general population data for each scale score.

$$\begin{aligned}
 PF_Z &= (PF - 84.52404) / 22.89490 \\
 RP_Z &= (RP - 81.19907) / 33.79729 \\
 BP_Z &= (BP - 75.49196) / 23.55879 \\
 GH_Z &= (GH - 72.21316) / 20.16964 \\
 VT_Z &= (VT - 61.05453) / 20.86942 \\
 SF_Z &= (SF - 83.59753) / 22.37642 \\
 RE_Z &= (RE - 81.29467) / 33.02717 \\
 MH_Z &= (MH - 74.84212) / 18.01189
 \end{aligned}$$

The z-scores for the raw scales will be combined to form the two raw summary scores by multiplying each one by its corresponding scoring coefficient from the general U.S. population and taking the sum of those values.

$$\begin{aligned}
 AGG_PHYS &= (PF_Z * .42402) + (RP_Z * .35119) + (BP_Z * .31754) \\
 &+ (GH_Z * .24954) + (VT_Z * .02877) + (SF_Z * -.00753) + (RE_Z \\
 &* -.19206) + (MH_Z * -.22069)
 \end{aligned}$$

$$\begin{aligned}
 AGG_MENT &= (PF_Z * -.22999) + (RP_Z * -.12329) + \\
 &(BP_Z * -.09731) + (GH_Z * -.01571) + (VT_Z * .23534) + (SF_Z * \\
 &.26876) + (RE_Z * .43407) + (MH_Z * .48581)
 \end{aligned}$$

The general U.S. population means, standard deviations, and scoring coefficients are summarized in the following table:

SF-36 Scale	Mean	SD	Factor Score Coefficients	
			PCS	MCS
PF	84.52404	22.89490	0.42402	-0.22999
RP	81.19907	33.79729	0.35119	-0.12329
BP	75.49196	23.55879	0.31754	-0.09731
GH	72.21316	20.16964	0.24954	-0.01571
VT	61.05453	20.86942	0.02877	0.23534
SF	83.59753	22.37642	-0.00753	0.26876
RE	81.29467	33.02717	-0.19206	0.43407
MH	74.84212	18.01189	-0.22069	0.48581

Finally, the PCS and MCS will be standardized as follows:

$$\text{PCS} = (\text{AGG_PHYS} \times 10) + 50$$

$$\text{MCS} = (\text{AGG_MENT} \times 10) + 50$$

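### SAP 10.4 defines the SF-36 raw scale score in two ways, and its only transform fits complete scales, so a scale with skipped items can be mis-scored or lost

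*SAP*

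**What the plan says.** SAP 10.4 first states that "the raw scale score will be calculated as the average score over non-missing items in that scale and scaled between 0 and 100", and that no score is calculated unless at least 50% "of relevant questions are answered in a scale domain". The following paragraph states: "The raw scale scores will be computed by taking the sum of the items for that particular scale". That sum then enters the only transform given: actual raw score minus lowest possible raw score, divided by the possible raw range, times 100. The bounds are tabulated by scale, for example 10 and 30 for Physical Functioning (PF), 2 and 12 for Bodily Pain (BP), and 2 and 10 for Social Functioning (SF).

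The same appendix has a separate recode of item 8, headed "If Item 7 is not answered", while the BP row of the table still adds items 7 and 8.

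For the component scores, SAP 10.4 says "The z-scores for the raw scales will be combined to form the two raw summary scores", and both printed formulas use all eight scales. SAP 10.1.2 adds: "The component scores will not be calculated unless all relevant domain scale scores are available". SAP 7.2, after its dynamometry rules, says: "Other efficacy endpoints will not be imputed".

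**The concern.** Nothing in SAP 10.4 converts the average to the sum metric or says how to sum when an item is blank. The 50% rule and the item 8 recode show that incomplete scales are meant to be scored, yet the printed sum-and-table step cannot do it. Taken literally, that step leaves two readings:

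- **Sum the answered items only.** The score is too low and can fall below 0. A change between visits in which items are skipped then looks like a change in quality of life.
- **A blank makes the sum missing.** A scale that the 50% rule keeps is lost, and that visit's PCS and MCS go with it.

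SAP 8.9 describes the exploratory analyses as mostly descriptive, but SAP 8.9.1 and 10.6 list GEE models for SF-36. In the efficacy model of SAP 8.8, "Changes from baseline will be the dependent variable, and baseline, visit will be the independent variables in the model", so a distorted or missing Baseline score affects every change value for that subject.

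**Working it through.** **Inputs, all from SAP 10.4.** The transform and bounds above. Item 8 values when item 7 is blank: 6.0, 4.75, 3.5, 2.25, 1.0. Item 6 final values: 5 to 1. SDs: BP 23.55879, SF 22.37642, PF 22.89490. Weights: BP 0.31754 and PF 0.42402 for PCS, SF 0.26876 for MCS. Each component score is the weighted sum of z-scores times 10, plus 50. A scale shift d therefore moves a component score by d / SD x weight x 10.

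**1. Reproduce the printed bounds** as number of items times lowest and highest item value. The item ranges for PF, RP and RE are inferred from the bounds.

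| Scale | Items | Item range | Bounds |
|---|---|---|---|
| PF | 10 | 1-3 | 10, 30 |
| RP | 4 | 1-2 | 4, 8 |
| BP | 2 | 1-6 | 2, 12 |
| GH | 5 | 1-5 | 5, 25 |
| VT | 4 | 1-6 | 4, 24 |
| SF | 2 | 1-5 | 2, 10 |
| RE | 3 | 1-2 | 3, 6 |
| MH | 5 | 1-6 | 5, 30 |

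All eight rows match, so every bound is a full-item sum.

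**2. Complete scales.** PF with all items at best: the sum rule gives (30 - 10)/20 x 100 = 100, and the average scaled on the item range gives (3 - 1)/2 x 100 = 100. The two rules agree. Putting the average itself into the printed transform gives (3 - 10)/20 x 100 = -35, so the average cannot be the raw score that the formula expects.

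**3. Skipped items, answered items summed.**

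BP, item 7 blank, item 8 value v. Sum: (v - 2)/10 x 100. Mean times 2 items: (2v - 2)/10 x 100.

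| v | Sum | Mean x 2 | Difference | PCS shift |
|---|---|---|---|---|
| 6.0 | 40 | 100 | -60 | -8.09 |
| 4.75 | 27.5 | 75 | -47.5 | -6.40 |
| 3.5 | 15 | 50 | -35 | -4.72 |
| 2.25 | 2.5 | 25 | -22.5 | -3.03 |
| 1.0 | -10 | 0 | -10 | -1.35 |

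First row: -60 / 23.55879 x 0.31754 x 10 = -8.09.

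SF, item 10 blank, item 6 value 5, 3 or 1: the sum gives 37.5, 12.5 or -12.5, and mean times 2 gives 100, 50 or 0. The differences -62.5, -37.5 and -12.5, each / 22.37642 x 0.26876 x 10, are -7.51, -4.50 and -1.50 MCS points.

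PF, one of ten blank, answered items averaging x: the error is -x/20 x 100, that is -5, -10 or -15 for x = 1, 2 or 3. Each / 22.89490 x 0.42402 x 10 gives -0.93, -1.85 or -2.78 PCS points.

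**4. Skipped items, blank makes the sum missing.** The eight scales use 10 + 4 + 2 + 5 + 4 + 2 + 3 + 5 = 35 items, and a blank in any one removes that visit's PCS and MCS. Each subject has four change values (Weeks 12, 24, 36, 48). A blank at one post-baseline visit loses 1 of 4. A blank at Baseline loses all 4, because SF-36 is not collected at Screening (SAP 10.5) and no earlier value can stand in.

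**5. Mean of answered items times number of items, in the printed transform.** Complete scales are unchanged. PF at best with one blank gives 3 x 10 = 30, hence 100, where summing nine items gives (27 - 10)/20 x 100 = 85. Scores stay within 0 to 100.

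**The case against.** The strongest reply is that one reading fits nearly all the text: average the answered items when at least half are present, place the result on 0 to 100, and treat the sum, formula and table as the arithmetic for complete scales. Negative scores would break the stated 0 to 100 range, and discarding incomplete scales would make the 50% rule and the item 8 recode pointless. SAP 10.1.2 also names the standard published algorithm as the basis for scoring. SAP 8.1 allows exceptions to its no-imputation rule where stated, so SAP 7.2 is no real bar. The largest shifts need a two-item scale half blank with the best answer on the other item. SF-36 is exploratory, is given only where a validated native-language version exists, and belongs to a single-arm study not powered for efficacy.

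Much of this stands. The intent is readable, the large figures are extremes, and the stakes are low. But the favourable reading must confine the sum sentence and table to complete scales, which the SAP does not say. The reference to the standard algorithm does not settle it within the documents, because SAP 10.1.2 sends the reader to Appendix 10.4 for the details. A range check would not reliably expose the error either: four of the five wrong BP values above lie between 0 and 100.

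**Conclusion.** The concern holds, as a minor point. SAP 10.4 gives two rules for the same quantity, and the sum rule as printed gives wrong or missing scores once an item is skipped. For an affected questionnaire, summing answered items shifts PCS by -1.3 to -8.1 (BP from item 8 alone) or -0.9 to -2.8 (one blank PF item), and MCS by -1.5 to -7.5 (SF from item 6 alone). For PF the low end is more relevant in this severely impaired population. Under the missing-sum reading, one blank item costs one or all four of a subject's PCS and MCS change values.

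This rests on the sum step being coded as printed. The documents give no skip rate, so the number of affected questionnaires cannot be stated and could be nil. Complete scales and the primary safety endpoint are not affected.

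**What to change.** In SAP 10.4, replace the averaging sentence, the 50% sentence and the sum sentence with one rule: if at least 50% of a scale's items are answered, the raw score is the mean of the answered items (after recoding) multiplied by the number of items in the scale, then transformed with the table; otherwise the scale is missing. Apply the item 8 recode for a blank item 7 before this step. In SAP 7.2, note that this is scale scoring and is not barred by the no-imputation statement.

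The cost is a few sentences and a check of the scoring code, with no change to data collection or to complete-scale scores. One drawback should be acknowledged: the rule assumes that skipped items resemble answered ones, so scores could be slightly high if subjects skip activities they cannot do.

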10.5 Schedule of Events

ASSESSMENTS AND EVENTS ^a	SCREENING ^b DAY -28 TO -4	BASELINE ^c	WEEK 12 VISIT (± 5 DAYS)	WEEK 24 VISIT (± 5 DAYS)	WEEK 36 VISIT (± 5 DAYS)	WEEK 48 VISIT (± 5 DAYS) OR EARLY TERMINATION VISIT ^d	SAFETY FOLLOW-UP ^r (TC)
INFORMED CONSENT	X						
INCLUSION/EXCLUSION CRITERIA	X	X					
DEMOGRAPHICS	X	X					
GNEM-SPECIFIC MEDICAL HISTORY ^e	X	X					
SAFETY ASSESSMENTS							
GENERAL MEDICAL HISTORY, HEIGHT ^f AND WEIGHT	X						
PRIOR AND CONCOMITANT MEDICATIONS AND THERAPIES	X	X	X	X	X	X	X
INTERVAL HISTORY ^g		X	X	X	X	X	
PHYSICAL EXAMINATION ^h	X	X	X	X	X	X	
VITAL SIGNS	X	X	X	X	X	X	
HEMATOLOGY, CHEMISTRY PANEL AND URINALYSIS ⁱ	X	X	X	X	X	X	
PREGNANCY TEST ^j	X	X	X	X	X	X	
THE COLUMBIA SUICIDE SEVERITY RATING SCALE	X	X	X	X	X	X	
ADVERSE EVENTS	X	X	X	X	X	X	X
URINE FOR MANNAC TESTING ^k	X	X	X	X	X	X	
BIOMARKERS: CK, SERUM SA, AND BIOMARKERS OF SIALYLATION AND OTHER BIOMARKERS ^l		X	X	X	X	X	

ASSESSMENTS AND EVENTS ^a	SCREENING ^b DAY -28 TO -4	BASELINE ^c	WEEK 12 VISIT (± 5 DAYS)	WEEK 24 VISIT (± 5 DAYS)	WEEK 36 VISIT (± 5 DAYS)	WEEK 48 VISIT (± 5 DAYS) OR EARLY TERMINATION VISIT ^d	SAFETY FOLLOW-UP ^e (TC)
CLINICAL ASSESSMENTS ^m							
MUSCLE STRENGTH TESTING BY HAND-HELD DYNAMOMETRY (HHD) ⁿ	X	X	X	X	X	X	
PATIENT-REPORTED OUTCOMES							
GNEM FUNCTIONAL ACTIVITIES SCALE (GNEM-FAS) – EXPANDED VERSION	X	X	X	X	X	X	
MEDICAL OUTCOMES SURVEY – 36 ITEM (SF-36) ^o		X	X	X	X	X	
PGI-S AND PGI-C ^p		X	X	X	X	X	
DISPENSE DRUG ^q		X	X	X	X		
TREATMENT COMPLIANCE		X	X	X	X	X	

^a Study assessments for a subject should be performed in a consistent order at each visit. Refer to the Clinical Evaluator Manual for additional details on specific assessments and the suggested order of administration.

^b Potential subjects can be screened up to 28 days before the Baseline Visit.

^c Baseline Visit should be at least 4 days after and within 28 days of Screening visit. Study drug will be dispensed only after all eligibility requirements are confirmed and study procedures at the Baseline Visit have been performed.

^d The Early Termination Visit occurs if a subject discontinues prior to completing the study or no longer wants to participate in the study. Every reasonable effort should be made to have subjects return to the clinic within 4 weeks of discontinuation and perform the Early Termination procedures; however, subjects who are unable to return to the clinic will be given the option of having an Early Termination Visit telephone call (TC) within 4 weeks of discontinuation from study, where appropriate information will be collected by the clinical site.

^e GNEM-specific medical history will include a detailed review of diagnostic and family history, as well as presenting symptoms and progression over time, and the use of assistive devices, drugs and therapies to manage the disease.

^f If a patient is unable to stand or has significant postural issues that interfere with collection of a standing height, self-reported adult height should be captured

^g Interval history will include any signs, symptoms, or events experienced by the subject since the prior study visit. Interval history may include exacerbation or improvement in existing medical conditions (including the clinical manifestations of GNEM) that might interfere with study participation, safety, and/or positively or negatively impact performance of functional assessments.

^h Complete physical examination including neurological examination conducted at Baseline and Week 48 (or Early Termination, if applicable) study visits. Brief physical examination at all other study visits.

ⁱ If urinalysis detects protein, leukocyte esterase, blood, or nitrite, urine microscopic examination will be conducted.

^j Pregnancy test by urine dipstick (local lab) is acceptable; a serum pregnancy test should be performed in the event of a positive or equivocal urine pregnancy test result.

^k An aliquot from the urine sample provided for the standard safety urinalysis testing will be used to test for the presence of ManNAc.

^l Serum will be obtained at all study visits to evaluate creatine kinase (CK), serum SA and potential biomarkers of sialylation, and other markers of muscle injury and remodeling.

^m The muscle strength (HHD) assessment will be administered to all subjects. The number of clinical assessments performed at each visit will be determined by the subject's extent of disease involvement. The physical therapist conducting the testing will choose the appropriate number and type of assessments guided by their clinical judgment, study training, and Clinical Evaluator Manual.

ⁿ Lower extremity muscle strength for knee extensors muscle group only.

^o The SF-36 will only be completed for subjects when a validated version is available in the subject's native language.

^p PGI-S (Patient global Impression of Severity) and PGI-C (Patient Global Impression of Change): PGI-S is to be administered only at baseline. PGI-C to be administered at all subsequent visits, including Early Termination.

^q Study drug will be dispensed only after all eligibility requirements are confirmed and study procedures at the Baseline Visit have been performed

^r This Safety Follow-up TC is to be completed only for subjects who complete the study and choose not to enroll in the extension study, UX001-CL302, or who discontinue the study early. This call is not required for subjects who are eligible and choose to take part in Study UX001-CL302. The site personnel should initiate the Safety Follow-up TC 30 (+5) days after a subject's last dose of study drug for subjects who complete the 48-week Treatment Period or 30 (+5) days after the ET Visit or ET TC for subjects who discontinue the study early. Information on any ongoing or new AEs, SAEs, and concomitant medications will be collected. Appropriate follow-up should continue until all safety concerns, in the Investigator's opinion, are resolved.

10.6 Summary of Efficacy Endpoints and Analyses

Test / Instrument	Endpoint	Type of analysis	Time points for Assessment	Statistical approach at week 48/ET analysis
GNEM Functional Activities Scale (GNEM-FAS) – Expanded Version	Change from baseline in GNEM-FAS Expanded Version total score and mobility, upper extremity and self-care domain scores from baseline over the duration of the study	Secondary efficacy analysis	Baseline, Weeks 12, 24, 36, and 48	GEE Model / Descriptive statistics
Physical therapy – Hand-held Dynamometry (HHD)	Change from baseline in upper extremity strength in the following muscle groups: grip, key pinch, shoulder abductors and wrist extensors over the duration of study	Secondary efficacy analysis	Baseline, Weeks 12, 24, 36, and 48	GEE Model / Descriptive statistics
	Change from baseline in lower extremity muscle strength in the knee extensors as measured by HHD over the duration of the study			
	% of Predicted Normal HHD Values			
Medical Outcome Survey – 36 Items (SF-36)	Change in health-related quality of life as assessed by using SF-36 over the duration of the study	Exploratory efficacy analysis	Baseline, Weeks 12, 24, 36, and 48	GEE Model / Descriptive statistics
Patient Global Impression of Severity & Change (PGI-S & PGI-C)	Change in symptom severity as measured by PGI-S (baseline only) and PGI-C over the duration of the study	Exploratory efficacy analysis	Baseline, Weeks 12, 24, 36, and 48	Descriptive statistics

10.7 Adverse Events to Monitor

10.7.1 Gastrointestinal MedDRA Query

The following MedDRA PTs are included in the gastrointestinal SMQ version 17.1.

Narrow Scope	Broad Scope
Abdominal discomfort	Anorectal swelling
Abdominal distension	Antacid therapy
Abdominal pain	Antidiarrhoeal supportive care
Abdominal pain lower	Antiemetic supportive care
Abdominal pain upper	Breath odour
Abdominal symptom	Chest pain
Abdominal tenderness	Colonic lavage
Abnormal faeces	Dysphagia
Aerophagia	Early satiety
Anorectal discomfort	Gastritis prophylaxis
Bowel movement irregularity	Gastrointestinal disorder therapy
Change of bowel habit	Gastrointestinal tract irritation
Constipation	Gastrooesophageal reflux prophylaxis
Defaecation urgency	Glycogenic acanthosis
Diarrhoea	Hypovolaemia
Epigastric discomfort	Laxative supportive care
Eruption	Malabsorption
Faecal volume decreased	Mucous stools
Faecal volume increased	Oesophageal polymer implantation
Faeces hard	Pernicious anaemia
Faeces soft	Post procedural constipation
Flatulence	Post procedural diarrhea
Frequent bowel movements	Post-tussive vomiting
Gastrointestinal pain	Probiotic therapy
Gastrointestinal sounds abnormal	Procedural nausea
Gastrointestinal toxicity	Procedural vomiting
Infrequent bowel movements	Prophylaxis against diarrhoea
Nausea	Prophylaxis of nausea and vomiting
Non-cardiac chest pain	Regurgitation
Oesophageal discomfort	Retching
Oesophageal pain	Steatorrhoea
Premenstrual cramps	Vomiting projectile
Vomiting	

10.7.2 Liver-Related Investigations

The following MedDRA PTs are included in the category “liver-related investigations.”

Alanine aminotransferase abnormal
Alanine aminotransferase increased
Aspartate aminotransferase abnormal
Aspartate aminotransferase increased
Gamma-glutamyl transferase abnormal
Gamma-glutamyl transferase increased
Hepatic enzyme abnormal
Hepatic enzyme increased
Liver function test abnormal
Transaminases abnormal
Transaminases increased
